11.2 Confinements and Visits

For all cohorts, subjects will be confined from the day before dosing (Day -1) until after the 48-hour post-start of infusion blood draw. Subjects will come back to the clinical site for all subsequent study assessments on Days 5 ± 1 , 8 ± 1 , 15 ± 1 , 22 ± 2 , 29 ± 2 , and 60 ± 3 (study exit or ET).

Participation of each subject in this study should last approximately 2 months.

11.3 Randomization and Blinding

Subjects will be administered each treatment (NS101 or placebo), according to the block randomization scheme. The subjects and the clinical personnel involved in the collection, monitoring, revision, or evaluation of AEs, or personnel who could have an impact on the outcome of the study will be blinded with respect to the subject's treatment assignment (NS101 or placebo). Blinding will be maintained at least until the clinical phase of the study is completed (i.e., when reporting and evaluation of all AEs have been completed, for all cohorts).

Designated pharmacy personnel at the clinical site not directly involved with the clinical aspects of the trial will prepare and dispense the study medication and will be aware of the randomization code. The study drug and placebo will have the same visual appearance in order to avoid compromising the study blinding.

A staggered dosing schedule will be used for each cohort and will include 2 sentinel subjects randomized in a 1:1 ratio (1 active and 1 placebo) dosed initially, and the remaining 6 subjects (5 active and 1 placebo) will be dosed at least 48 hours later.

One randomization scheme will be produced for each cohort separately.

Within each cohort in Cohorts 5 to 8, subjects will be randomized a second time to one (1) unique timepoint for collection of a CSF sample (via lumbar puncture). Each of the 4 timepoints specified in section 11.8.3 will be assigned to 2 subjects. Sentinel subjects will be randomized to the same timepoint, to ensure that each timepoint is assigned to at least 1 subject that is on active drug. Although lumbar puncture is planned starting from Cohort 5, cumulative safety/tolerability data from previous cohorts will inform on whether lumbar puncture will be started at Cohort #5.

In the event of an emergency for an individual subject in which knowledge of the study treatment is critical to the subject's medical management or for the decision of dose escalation, the Investigator may break the blind for that subject. An envelope for each subject containing the treatment assignment will be available from the pharmacy personnel. The Investigator or other attending study physician will make every effort to contact the Sponsor prior to unblinding a subject's treatment assignment and will record the date and reason for unblinding in the study source documents.

As all samples (including placebos) will be analyzed, the randomization code will not be available to the Bioanalytical Division of Syneos Health prior to analysis from each cohort. However, since concentrations of NS101 above the analytical method's lower limit of quantification (LLOQ) should not be observed for subjects receiving the placebo, blinding of treatment assignments by personnel in the Bioanalytical Division involved with sample analysis cannot be assured completely.

Blinded PK results will be available during the course of the study. These results will be reported without revealing the subject's identity.

11.4 Investigational Products

Active ingredient, NS101: NS101 solution for injection in glass vial and developed in

400 mg/16 mL (25 mg/mL) strength, Manufactured by BINEX Co., Ltd. and supplied in 20 mL glass injection vials (Neuracle Science Co., LTD., Republic of Korea) Details in Table 9 and

Table 10.

Placebo for NS101: Matching placebo solution without the active component,

composed of the same ingredients as NS101 solution for IV injection, with the same visual appearance once diluted. To be supplied in 20 mL glass injection vials. Manufactured by BINEX Co., Ltd. and supplied in 20 mL glass injection vials (Neuracle

Science Co., LTD., Republic of Korea) Details in Table 11.

Table 9. List of General Physicochemical, Biological and Immunochemical Properties of NS101

Appearance	Clear, colorless or yellowish solution			
Molecular Weight	~146 kDa			
pI of main band	Theoretical pI: 5.56, IEF gel: pI 4.5 – 7.4			
Number of amino acids	Heavy chain (HC): 461 amino acids			
	Light chain (LC): 214 amino acids			
Polypeptide chain composition	Two (2) hetero dimers, each comprising an HC and LC			
Disulfide bonds	Four (4) intra-chain LC disulfide bonds; two per light LC			
	Ten (10) intra-chain HC disulfide bonds: five per HC			
	Two (2) inter-chain disulfide bonds between the two HC			
	Two (2) inter-chain disulfide bonds; one each between			
	HC and LC			
Secondary structure (by circular	α-helix: 6.8%			
dichroism analysis)	β-sheet (anti-parallel and parallel): 47.9 – 48.5%			
	β-turn: 14.8%			
	random coil: 32.1 – 32.4%			
Potency (ELISA)	70-130%			
Binding specificity	Specific binding to FAM19A5			

Table 10. Composition of NS101

Component	Quantity per Vial	Final Concentration	Function	Quality Standard
NS101 Active substance	400 mg	25 mg/mL	Active substance	In-house
L-Histidine-HCl	24.824 mg	10 mM	Buffer	EP

Hydrochloric acid	q.s.		pH modifier	EP
Polysorbate 20	1.6 mg	0.01%	Surfactant	EP
Sodium chloride	140.256 mg	150 mM	Isotonic agent	EP
Water for injection	q. s. to 16.0 mL		Solvent	EP

Table 11. Composition of Placebo for NS101

NS101 Placebo is a sterile preservative-free solution for IV infusion in colorless glass vial (USP type I glass vial, 20mL). A 20 mL glass vial contains 16 mL of NS101 Placebo solution for injection.

Component	Quantity/vial	Function	Specification
L-Histidine	24.824 mg	Buffer	EP
Hydrochloric acid	q.s.	pH modifier	EP
Polysorbate 20	1.6 mg	Surfactant	EP
Sodium chloride	140.256 mg	Isotonic agent	EP
Water for injection	q.s. to 16.0 mL	Solvent	EP

11.5 Drug Supplies and Accountability

It is the responsibility of the Sponsor to ensure that study medication provided for this study are manufactured under Good Manufacturing Practice (GMP) and are suitable for human use. The Sponsor is responsible to ship a sufficient amount of dosage units to allow the clinical site to maintain an appropriate sampling for the study.

Study medication will be stored at the clinical site as per applicable requirements. The medications will be stored in a locked, environmentally-controlled medication room with restricted access. Container(s) will bear a label containing at least the name of the study drug, lot and/or batch number, and manufacturing and expiry date.

Individual doses for each subject will be dispensed at the clinical site, as per appropriate SOP. Individual doses will be dispensed according to the randomization scheme in appropriate dosing containers indicated with at least the project number, the cohort number and the subject number/spare number.

All study drug received at the site will be inventoried and accounted for throughout the study and the result recorded in the drug accountability/retention record according to the clinical site appropriate SOP. At the end of the study, used vials will be destroyed at the clinical site as per clinical site SOP.

NS101 and placebo for NS101 should be refrigerated at 2-8°C and should not be frozen. NS101 was stable for 18 months without any significant changes in quality. NS101 is being monitored for stability at the long-term storage condition of 5±3°C for 36 months.¹

11.6 Study Treatments Administration

The study treatment will be administered in bed by IV infusion using aseptic techniques. Detailed instructions for study treatment infusion will be included in Pharmacy forms and/or Project Specific Procedure (PSP).

The body weight of each subject measured on Day -1 (check-in) will be used to calculate the exact individual dose required on a mg/kg basis, based on their assigned dose level (cohort), as presented in Table 12. The infusion will be performed over a period of approximately 60 minutes at a constant rate using a volume-controlled infusion device.

Table 12. Dose Levels per Cohort

Cohort	Dose levels of NS101*
1	1 x 0.25 mg/kg
2	1 x 0.75 mg/kg
3	1 x 1.50 mg/kg
4	1 x 3.0 mg/kg
5	1 x 6.0 mg/kg
6	1 x 12.0 mg/kg
7	1 x 24.0 mg/kg
8	1 x 48.0 mg/kg

^{*} Volume of NS101 placebo will be also determined based on subject weight and NS101 concentration.

As an example, for a human weighing 60 kg assigned to the first dose level of 0.25 mg/kg, the administered dose would be equal to 15 mg.

Approximately 1 hour prior to start of study drug infusion, an IV port will be inserted into the antecubital region and a sterile normal saline solution infusion will be initiated at fixed rate in order to keep the vein open. The study drug will be infused over approximately 60 minutes at a constant rate. At the end of the infusion, 3 mL of saline solution will be injected to flush the remaining drug into the IV catheter. The end of infusion will be set to the end of the 3 mL flush. For safety reason (e.g., administration of rescue medication), the IV line will remain opened for approximately 1 hour following completion of infusion.

The start and end times of infusion of each subject will be recorded in the source documents. Time of dosing will be set as the start of study treatment infusion.

Diluted NS101 should be used within 4 hours at room temperature. Diluted NS101 stored at 2°C to 8°C should be equilibrated to room temperature for 30 minutes prior to infusion.

11.7 Study Restrictions

11.7.1 Food and Fluids

For standardization purposes, no food will be allowed from at least 8 hours prior to start of infusion until at least 2 hours after the start of study drug infusion. A light meal will be served more than 2 hours after the start of study treatment infusion.

Water will be provided *ad libitum* at all times.

In addition, subjects will be required to abstain from:

- food containing poppy seeds within 24 hours prior to admission;
- food or beverages containing xanthine derivatives or xanthine-related compounds or energy drinks from 48 hours prior to dosing and during confinement.

11.7.2 Tobacco, Alcohol, and Illicit Drugs

Subjects will be required to abstain from using soft or hard drugs or any tobacco or nicotine products from screening and throughout the study.

Consumption of alcohol-based products will be prohibited from 24 hours prior to admission, and 24 hours prior to any study assessment visit.

11.7.3 Concomitant Medications

Subjects will be required to avoid using prescription and over-the-counter medications for the period of time specified in exclusion criterion #8) and throughout the study. Subjects will be required to avoid using natural health products (including herbal remedies, homeopathic and traditional medicines, probiotics, food supplements such as vitamins, minerals, amino acids, essential fatty acids, and protein supplements used in sports) from 7 days prior to dosing and throughout the study.

No concomitant medications are allowed during the study, with the exception of one(s) required for the medical management of an AE, medications exempted by the Investigator on a case-by-case basis that are judged unlikely to affect the PK profile of the study drug or subject safety (e.g., topical drug products without significant systemic absorption) and occasional use of acetaminophen.

Subjects will also be required to avoid receiving any vaccination, including COVID-19 vaccine, from 14 days prior to dosing and throughout the study. If vaccination is required for any reason, it must first be discussed with and exempted by the Investigator on a case-by-case basis to ensure that it does not compromise the PK profile of the study drug or the subject safety.

All medications taken by subjects after screening until the last study day will be documented as concomitant medications. Any concomitant medication use, other than the allowed medications stated above, will be reviewed and evaluated on a case-by-case basis by the Investigator to

determine if they affect a subject's eligibility or continued participation in the study, or for potential impact on the study results.

11.7.4 Posture and Physical Activity

For safety reasons, subjects will be required to remain supine and avoid sleeping from approximately 1 hour before start of infusion until after the first 4 hours after start of study drug infusion.

However, failure of subjects to comply with these requirements does not constitute a deviation from the protocol if it is medically necessary, required for procedures, or to go to the bathroom. When appropriate, subjects will be accompanied by a staff member while walking. Vigorous activity will be prohibited at all times during the confinement.

11.7.5 Other Restrictions

Only for cohorts undergoing lumbar puncture (Cohorts 5 to 8), subjects will be asked not to wear artificial nails or nail polish on days of pulse oximetry during lumbar puncture (Days 2, 8, and 15), at least on the fingers used for PO monitoring, in order to avoid false readings.

11.8 Sample Collection and Processing

11.8.1 Blood Sampling for PK Analysis

A total of 21 blood samples will be collected in each cohort for PK analysis: pre-start of infusion and $0.25 (\pm 3 \text{ min})$, $0.5 (\pm 3 \text{ min})$, $0.75 (\pm 3 \text{ min})$, $1 (\pm 3 \text{ min})$, $1.25 (\pm 3 \text{ min})$, $1.5 (\pm 3 \text{ min})$, $2 (\pm 3 \text{ min})$, $4 (\pm 15 \text{ min})$

11.8.2 Blood Sampling for PD Analysis

A total of 14 blood samples will be collected in each cohort for PD analysis: pre-dose and 1, 4, 6, 12, 24 (Day 2), 36 (Day 2), 48 (Day 3), 96 (Day 5±1), 168 (Day 8±1), 336 (Day 15±1), 504 (Day 22±2), 672 (Day 29±2), and 1416 (Day 60±3) hours post-start of infusion (3 mL for each sampling time).

11.8.3 Lumbar Puncture for CSF Sampling

For Cohorts 5 to 8 only: for each subject, a single CSF sample will be collected via lumbar puncture for PK and PD analysis. The volume of collected CSF per sample should not exceed approximately 6 mL.

Subjects in each cohort will be randomized to have their CSF sample collected at one of the following timepoints, so as to have 2 subjects assigned to each timepoint: 24 (±3 hours; Day 2), 36 (±3 hours; Day 2), 168 (Day 8±1), or 336 (Day 15±1) hours post-start of infusion, according to

the randomization scheme. Sentinel subjects will be randomized to the same timepoint. Placebo subjects will serve to evaluate change from baseline.

Lumbar puncture may require administration of a local anesthetic, such as lidocaine. Details would be described in a separate document.

A catheter will be inserted during the procedure for safety.

Following the lumbar puncture, subjects could be observed for up to 6 hours while in supine position. The Investigator or designee will then assess the subject to determine whether it is safe for them to leave the clinic. If there is a safety concern, the Investigator or designee can request the subject to remain for further monitoring as needed. Subjects should refrain from physically strenuous activities for 12 hours after lumbar puncture and may then resume their usual routines.

Vital signs will be also measured before lumbar puncture and will be measured approximately 0.5 hours after lumbar puncture, meaning approximately 24.5 (±3 hours; Day 2), 36.5 (±3 hours; Day 2), 168.5 (Day 8±1), or 336.5 (Day 15±1) hours post-start of infusion, according to the randomization scheme.

PO will be performed during lumbar puncture: 24 (±3 hours; Day 2), 36 (±3 hours; Day 2), 168 (Day 8±1), or 336 (Day 15±1) hours post-start of infusion, according to the randomization scheme.

Details will be included in the PSP.

Cumulative safety/tolerability data from early cohorts will inform on whether lumbar puncture will be started at Cohort 5.

11.8.4 Anti-Drug Antibody Measurement (Immunogencity)

A total of 6 immunogenicity blood samples will be collected for ADA and NAbs: pre-start of infusion and 96 (Day 5±1), 336 (Days 15±1), 504 (Day 22±2), 672 (Day 29±2), and 1416 (Day 60±3) hours post-start of infusion (3 mL for each sampling time).

11.8.5 Time Tolerance Windows and Total Blood Volume

The time tolerance window for blood samples collected during the confinement period will be within the hour pre-dose for the pre-infusion sample, ± 3 minute for all samples collected before 8 hours post-start of infusion and ± 15 minutes for all subsequent samples collected up to 48 hours post-start of infusion. The time tolerance window for return visit samples will be ± 1 day on Days 5, 8 and 15, ± 2 days for Days 22 and 29, and ± 3 days for Day 60. The time tolerance window for CSF samples on Day 2 is ± 3 hours. Sample collections done outside the pre-defined time windows will not be considered as protocol deviations since actual post-start of infusion sampling times will be used for PK and statistical analyses. Unless otherwise specified or for subject safety, when blood draws and other procedures coincide, blood draws will have precedence. When timepoints for ECGs, vital signs, and blood draws coincide, procedures will be carried out in the said order. A dead-volume intravenous catheter will be used for blood collection to avoid multiple skin punctures, when appropriate. Otherwise, blood samples will be collected by direct venipuncture.

The planned volume of blood to be collected during the study, including that collected for eligibility and safety purposes, should not exceed 250 mL. Additional tests or blood draws could be performed, if deemed required by the Investigator or study staff.

Serum and CSF samples will be collected and processed as per the Analytical Methodology Information Sheet / Laboratory Manual.

11.9 Subject Monitoring

Subjects will be monitored throughout the study by the clinical staff for AEs. In each cohort, the Investigator or designee will be on site one hour prior to the start of treatment infusion and until 5 hours post-start of infusion, and available on call for the remainder of the study. If necessary, the Investigator or designee at the clinical site or a healthcare professional in a nearby hospital will administer treatment for any AE(s). A crash cart or emergency bag containing the necessary rescue material and appropriate medications will be available in the clinic to allow rapid intervention in case of emergency.

Safety parameters, including laboratory results and ECG, will be assessed by the Investigator or designee, using the clinical site's criteria for biomedical laboratory and ECG acceptance ranges as suggested guidelines in making the medical assessment.

Scheduled safety measurements will be repeated according to the clinical site SOPs or upon request from the Investigator or designee. Any abnormal repeated measurement will be evaluated by the Investigator or designee and repeated if judged necessary. Further action may be taken upon the Investigator or designee's request.

Subjects will be advised to notify their healthcare professional(s) (e.g., physician, dentist, and/or pharmacist) that they are participating in a clinical research study on a drug being developed by Neuracle Science Co., LTD. for the potential clinical use in adult patients with neurodegenerative diseases, including AD, ALS, and SCI, called NS101, before taking any medicines or undergoing any medical procedure.

11.9.1 Vital Signs

BP, HR, RR, and OT will be measured in a sitting position (except for safety reasons) at screening and at study exit.

BP, HR, RR, and OT will also be measured on Day -1. BP, HR, and OT will also be measured on Day 1 pre-infusion and 1.5, 2, 4, 6, 8, 12, 24 (Day 2) and 48 (Day 3) hours post-start of infusion, and on Days 5 ± 1 , 8 ± 1 , 15 ± 1 , 22 ± 2 , and 29 ± 2 . BP, HR, RR, and OT will be measured in a supine position during confinement.

When vital signs measurements coincide with a blood draw, they should preferably be performed before the blood collection whenever possible.

11.9.2 12-lead ECG

Supine 12-lead ECG will be performed at screening and study exit.

Supine ECG will also be performed on Day 1 pre-infusion and 1.5, 4, 8, 12, 24 (Day 2), and 48 (Day 3) hours post-start of infusion, and on Days 5 ± 1 , 8 ± 1 , 15 ± 1 , 22 ± 2 , and 29 ± 2 .

When ECG coincides with a blood draw, it should preferably be performed before the blood collection whenever possible.

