	After database lock, the power model approach will also be performed on AUC_{0-24} , AUC_{0-in} , AUC_{0-inf} , and C_{max} data to assess the dose-proportionality when all dose levels will be completed. Non-parametric analysis will also be performed on the untransformed T_{max} data.

Immunogenicity:
Incidence and titer of ADAs and NAbs will be assessed.

4. Schedule of Events

	Screening				Co	ohorts 1 to	81				Study Exit
PROCEDURE	D-28 to D-2	D-1	D1	D2	D3	D5±1	D8±1	D15±1	D22±2	D29±2	(Day 60 ± 3) or E.T.
Informed Consent	X										
Demographic Data	X										
Medical and Medication Histories	X										
Review and Monitoring of AEs and Concomitant Medications	X	X	X	X	X	X	X	X	X	X	X
Physical Examination ²	X	X			X		X	X			X
Body Measurements ³	X	X									
Vital Signs (BP, HR, RR, OT) ⁴	X	X	X	X^{13}	X	X	X^{13}	X^{13}	X	X	X
ECG	X		X^5	X^5	X ⁵	X	X	X	X	X	X
S-STS	X										X
Hematology	X	X^6			X		X	X		X	X
Biochemistry	X	X^6			X		X	X		X	X
Coagulation	X	X^6			X		X	X		X	X
Serology (HIV and Hepatitis B and C)	X										
Urinalysis	X	X^6			X		X	X		X	X
Urine Drug Screen	X	X									
Alcohol Breath Test	X	X									
Confinement		X	X	X	X						
Randomization			X^7								
Injection Site Evaluation			X^8	X^8	X^8	X^8	X^8				
Study Treatment Administration			X^9								
Blood PK Samples ¹⁰			X	X	X	X	X	X	X	X	X
Blood PD Samples ¹¹			X	X	X	X	X	X	X	X	X
Lumbar Puncture for CSF Samples ¹²				X			X	X			
Pulse oximetry (PO) ¹⁴				X			X	X			
Blood Samples for ADA Assessment ¹⁵			X			X		X	X	X	X

- 1 Dose escalation will not occur until safety and tolerability up to Day 8±1 and available PK data up to 48 hours post-start of infusion for at least 7 subjects are assessed in the preceding cohort, and the study drug is deemed safe by the SRC.
- 2 A complete physical examination will be performed at screening and study exit. A brief physical examination will be performed on Day -1, Day 3 (approximately 48 hours post-start of infusion), Day 8±1, and Day 15±1, and as symptoms directed.
- 3 Height, weight, and BMI will be collected at screening. Body weight will be collected on Day -1 to calculate the dose to be administered per subject.
- 4 BP, HR, RR, and OT: screening, Day -1, and study exit. BP, HR, and OT: Day 1 pre-start of infusion and 1.5, 2, 4, 6, 8, 12, 24 (Day 2), and 48 (Day 3) hours post-start of infusion, as well as on Days 5 ±1, 8±1, 15±1, 22±2, and 29±2.
- 5 ECG: Day 1 pre-infusion and 1.5, 4, 8, 12, 24 (Day 2), and 48 (Day 3) hours post-start of infusion.

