5.4.1 Anticipated Clinical Risks and Benefits

Healthy subjects will not benefit from this study. However, the data from this study may be potentially helpful for future subjects with AD, ALS, or SCI.

Anticipated clinical risks include the following:

• The human-equivalent doses of the two concentrations (10 ug/mL and 100 ug/mL) at which cytokine release may be expected (section 5.2.6) were calculated and found to be 0.375 ~ 3.75 mg/kg in adult males. NS101 in comparison to cetuximab showed slightly higher level of IL-8, and TNF-α; however, the extent of this level was statistically insignificant. For this FIH study, the maximum selected dose is 12 mg/kg, and, from this dose, the expected C_{max} should be approximately 31 ug/mL. Some level of cytokine release may be expected due to the expected C_{max} concentration. With reference to the cytokine profile of NS101 from previous study, we may predict slightly higher level of cytokine release than that of cetuximab.

Accordingly, infusion-related reactions will be carefully monitored throughout the study.

 Acute reactions following infusion of monoclonal antibodies can be caused by various mechanisms, including acute anaphylactic (IgE-mediated) reactions, serum sickness, tumor lysis syndrome (TLS) and cytokine release syndrome (CRS). Clinical manifestations may include local skin reactions at the injection site, pyrexia and an influenza-like syndrome, to acute anaphylaxis and systemic inflammatory response syndrome. Infusion reactions may occur after NS101 administration.

This can be managed by recognition of risk factors, appropriate monitoring and prompt intervention. Appropriate hydration and diuresis, premedication and cautious incremental increases in the rate of infusion can minimize risk.

• Lumbar puncture, planned for the current study, may cause headache due to leakage of fluid, pain, bleeding, and brainstem herniation. Subjects will remain at the clinic for a sufficient period of time after the procedure for adequate monitoring.

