5.4.3 Rationale for the Study Population

A male healthy volunteer population has been selected for the study because healthy subjects with no concomitant diseases and using no concomitant medications represent a homogenous population allowing for proper evaluation of the safety, tolerability, and PK of a drug without confounding factors.

No reproductive studies have been conducted in NS101. Since risks to a developing foetus or reproductive effects are not known, only male subjects will be included in the study. Furthermore, non-vasectomized male subjects with a female partner of childbearing potential will be required to use an appropriate method of contraception, and will be restricted from sperm donation.

6. Objectives

Primary objective:

To assess the safety and tolerability of NS101 following IV administration of single ascending doses in healthy subjects.

Secondary objectives:

- To characterize the PK profile of NS101 in serum and NS101 concentrations in CSF following single IV infusion doses in healthy subjects.
- To characterize the PD profile of NS101 through FAM19A5 in plasma and FAM19A5 concentrations in CSF following single IV infusion doses in healthy subjects.
- To evaluate the immunogenicity profile of NS101.

7. Study Endpoints

Primary endpoints:

- Incidence, nature, relatedness, and severity of AEs.
- Changes in vital signs measurements, physical examination, clinical laboratory test findings, 12-lead-ECG.

Secondary endpoints:

- Serum PK parameters for NS101 will include: AUC_{0-24} , AUC_{0-t} , AUC_{inf} , C_{max} , T_{max} , $T_{\frac{1}{2}}$ el, K_{el} , Cl, and V_z .
- Concentrations of NS101 in CSF.
- Serum to CSF ratio of NS101 concentrations.
- Immunogenicity of NS101, measured as the number and percentage of subjects who develop detectable ADAs and NAbs.

[figure not shown]
Exploratory endpoints:

- Effect (E): variation of level of FAM19A5 (Δ FAM19A5) following administration of NS101:
 - o PD: Change in baseline of FAM19A5 levels
 - o PD parameters in plasma: AUEC_{0-t}, E_{max} , and TE_{max} .
 - o Concentrations of FAM19A5 in CSF.

8. Study Design

This will be a single center, Phase 1, double-blind, randomized, placebo-controlled, sequential SAD study (Figure 9). The study will consist of **8** cohorts (Cohorts 1 to **8**).

Figure 9. Study Diagram

8.1 Design for Cohorts 1 to 8

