11.11 Study Exit Procedures and ET

Complete physical examination, hematology, biochemistry, coagulation, urinalysis, vital signs (BP, HR, RR, and OT), S-STS, ECG, and AE monitoring, as well as collection of PK, PD, and immunogenicity samples, will be performed on the last study visit (Day 60 ± 3). If not possible, all efforts will be made to complete study exit procedures within 14 days after the last participation of the subject in the study.

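### Respiratory rate belongs to the vital-signs primary endpoint but is recorded in only 1 of 14 routine post-dose sets, none of them on Day 1 or through Day 29

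*Protocol*

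**What the plan says.** Protocol section 7 lists among the primary endpoints "Changes in vital signs measurements, physical examination, clinical laboratory test findings, 12-lead-ECG", and SAP section 4 repeats it. The endpoint does not name its components, but section 11.11 does: "vital signs (BP, HR, RR, and OT), S-STS, ECG, and AE monitoring". The screening list in section 11.1 gives the same four.

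Section 11.9.1 sets the timing. Before dosing, "BP, HR, RR, and OT will also be measured on Day -1". From then on RR is left out: "BP, HR, and OT will also be measured on Day 1 pre-infusion and 1.5, 2, 4, 6, 8, 12", and so on to 24 and 48 hours and Days 5, 8, 15, 22 and 29. RR returns at study exit. Footnote 4 of the Schedule of Events says the same: "BP, HR, RR, and OT: screening, Day -1, and study exit". The synopsis, under Subject Monitoring, also limits the Day 1 to Day 29 sets to blood pressure, heart rate and temperature.

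Three other texts are less clear:

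- The Schedule of Events row is labelled "Vital Signs (BP, HR, RR, OT" and is ticked at every visit, subject to footnote 4.
- Section 11.9.1 also says "BP, HR, RR, and OT will be measured in a supine position during confinement", without giving RR times. The same section has subjects sitting at screening and exit.
- In Cohorts 5 to 8, vital signs are taken before and about half an hour after lumbar puncture (Schedule footnote 13, section 11.8.3), with no components named.

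SAP section 6.3 takes as baseline the latest available value before the infusion. SAP section 11.4 summarises change from baseline at each time point and has no separate rule for RR.

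**The concern.** Protocol section 5.4.1 discusses acute reactions to monoclonal antibodies, including anaphylaxis and cytokine release, and says "Infusion reactions may occur after NS101 administration". Those reactions belong to the infusion and the hours after it. One of the four vital signs in the primary endpoint has no scheduled value in that period.

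Two uses of the data suffer. First, the final report: the RR part of the endpoint rests on one comparison about two months apart, which cannot describe an acute effect at any dose level against placebo. Second, escalation: the SRC meets on data to about Day 8 (section 9.1), and section 9.2.3.1 includes vital-sign abnormalities among the events that halt escalation. On the routine schedule no post-dose RR exists by then, so scheduled RR cannot inform that criterion.

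**Working it through.** The plan gives no figure to reproduce here. The check is a count of scheduled sets from section 11.9.1 and Schedule footnote 4, then a reading of what the SAP can do with them.

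**Blood pressure, heart rate, temperature**
- Pre-dose: screening, Day -1, Day 1 pre-infusion = 3.
- Post-dose: 1.5, 2, 4, 6, 8, 12, 24, 48 h = 8; Days 5, 8, 15, 22, 29 = 5; exit = 1. Sum 8 + 5 + 1 = 14.
- Total 3 + 14 = 17.

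**RR**
- Pre-dose: screening, Day -1 = 2.
- Post-dose: exit = 1, nominally 1416 h.
- Total 2 + 1 = 3, so RR is in 1 of 14 routine post-dose sets and missing from 13.

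**Possible additions**
- Lumbar puncture, Cohorts 5 to 8 only: if vital signs there include RR, 2 readings per subject, the earliest at nominal 24 h. Two subjects are assigned to each of 24, 36, 168 and 336 h, so at most 2 + 2 + 2 = 6 of 8 subjects in a cohort would have such readings by about Day 8. In Cohorts 1 to 4 there are none.
- Early termination: exit procedures are done at withdrawal, so a withdrawn subject would have an earlier RR.
- Neither source gives a scheduled RR in the first hours after infusion.

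**What the SAP comparison becomes**
- Baseline: with no Day 1 RR, the latest scheduled pre-infusion value is Day -1. Confinement starts on Day -1 (section 11.2), so that value is supine.
- Post-baseline: exit, sitting.
- The one routine RR change therefore combines about 60 days with a change of posture, and the SAP does not address the posture difference.
- An RR taken ad hoc during a reaction would be an unscheduled value. SAP section 6.2 keeps those in listings and out of the summary tables.

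**Timing against exposure (illustration only)**
- Section 8.1 cites a half-life of 329.9 h, seen in mice and thought possible in humans. If it applied, 1416 / 329.9 = 4.29 half-lives, and 0.5^4.29 = 0.051, so about 5% of drug would remain at the only routine post-dose RR.
- The point does not depend on this figure.

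**The case against.** The best defence is that the omission is consistent and deliberate. The synopsis, footnote 4 and section 11.9.1 all give the same RR times. The row label carries footnote 4, and the table narrows other rows in the same way: body measurements are ticked on Day -1, but footnote 3 limits that day to weight. The supine sentence is compatible too, because Day -1 falls within confinement. The endpoint does not require every component at every time point. The monkey safety-pharmacology study (section 5.2.2) found no drug-related change in respiratory parameters; its findings were in heart rate, with an accompanying QT change, and in body temperature. Heart rate and temperature are in every set here.

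Much of this stands. A reader might infer that the row label shows RR was meant at every visit. The documents do not support that, since a footnoted label does not override three matching statements. A reader might also infer that no respiratory change could be seen at all. That goes too far: section 11.10 requires close observation for infusion reactions, section 11.9.3 has the chest and lungs examined on Days 3, 8 and 15 and as symptoms direct, and adverse events are collected throughout and are themselves a primary endpoint. Nor would an early RR effect be reported as no change. SAP section 6.4 does not impute, so the values would simply be absent.

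What the defence does not supply is a measured RR series comparable with placebo, or a stated reason for omitting one. Consistency shows what the schedule is, not that it serves the endpoint.

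**Conclusion.** The point holds in limited form. On the routine schedule RR is in 1 of 14 post-dose sets, with none on Day 1 or at the visits through Day 29. The RR part of the vital-signs endpoint is a supine Day -1 value against a sitting exit value, which cannot support a conclusion about acute respiratory change. Routine RR also cannot inform the SRC's vital-sign criterion.

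This rests on two readings: that vital signs in the endpoint means the four components listed in sections 11.1 and 11.11, and that footnote 4 governs the schedule row. If lumbar-puncture vital signs include RR, Cohorts 5 to 8 gain up to 2 readings per subject, none scheduled before nominal 24 h.

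The gap is in measured RR data, not in respiratory surveillance as a whole. It is worth correcting because the correction is cheap, not because the safety assessment fails without it.

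**What to change.** Reconcile the Schedule of Events row, footnote 4, the synopsis, section 11.9.1 (including its sentence on supine measurement in confinement) and the lumbar-puncture footnote, in one of two ways.

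1. **Record RR as endpoint data with each existing blood pressure, heart rate and temperature set**, including Day 1 pre-infusion, which becomes a same-day supine baseline. This adds 13 post-dose values and 1 pre-dose value per subject, or 14 × 64 = 896 short readings if applied to all 64 planned subjects. It needs amendment wording and an RR entry with sets already taken, but no new visit, device or staff. It gives no reading during the infusion, because the first post-dose set is at 1.5 h and the infusion lasts about 1 h. The current amendment says results up to Cohort 4 were already available, so only later cohorts could gain. If it applied from Cohort 5, the pooled placebo RR series would come from 4 × 2 = 8 subjects instead of 8 × 2 = 16.

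2. **If the omission is deliberate, or for cohorts already dosed**, correct the row label and have the SAP state that RR change is Day -1 versus exit only, in different positions, and does not support a conclusion about acute respiratory change. This costs wording alone.

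Under either option, state whether the lumbar-puncture vital signs include RR and how those values, and any from early termination, enter the summaries.
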